7. CONSENT PROCESS

Consent is an on-going process that starts when an intervention subject is first informed about the study and ends when the intervention subject's study participation is completed.

Verbal Consent for Phone and In-Person screening: When potential participants contact us, the study staff will first explain the study and obtain their verbal consent to proceed with phone screening, using the phone screening script. A waiver of documentation of consent has been requested for this step because it is conducted over-the-phone so participants will not be able to sign this consent themselves. Staff will also obtain verbal consent from the participants' study partner subjects before proceeding with their part of the phone screening. During phone screening, the opportunity to complete secondary screening and assessments over the phone will be offered.

EDRA Recruiters: Participants who are recruited through the EDRA program will have their initial phone screening materials and verbal consents completed by the ED recruiters. ED recruiters will undergo training by lab staff in order to administer this measures. Participants recruited this way will also sign a permission to contact form to allow lab staff to contact for additional study measures and enrollment procedures.

Consent and Re-consent: The initial signed paper consent will be obtained during the in-person interview by the intervention subject. (Screening Step 2). The partner subject will be consented either at an in-person appointment or via the mail if secondary screening appointment is completed over the phone. Secondary screening over the phone is included to ensure partner subject safety. The intervention subject and study partner subject may complete their secondary screening appointment and consented on separate dates. If the intervention subject completes their in-person screening appointment first and is deemed ineligible, the study partner subject will not proceed with their secondary screening and will not be consented to the study.

- 1) Explanation of the study: During the second screening interview, the

staff will explain the study in detail to the participants and their study partner subject, including the study purpose, procedures, time commitment, randomization, data collection, risks, benefits, privacy, confidentiality, compensation, voluntary nature, and contact persons for questions and concerns. Emphasis will be placed on explaining the risks. Questions will be answered and any confusion about the study will be resolved.

- 2) Assessment of capacity to consent: The staff will assess the potential intervention subject's capacity to consent using the UCSD Brief Assessment of Capacity to Consent form (UBACC) for the study. A score of 2 on items 1, 2, 4, 6, 7, and 9 is needed for inclusion in the study. If a participant scores less than 2 on any item, the staff will re-explain the study and reevaluate the capacity of the subject. Given the potential fluctuation of their cognitive capacity, if a subject still fails to score 2 on required items, we will ask the person to return on another day to re-take the UBACC. If the subject still scores below 2 on any required item during the 2nd visit, he/she cannot be enrolled in the study. Of note, other items than the required 6 items are provided for education purpose. If they do not answer 2 on those items, the staff will re-explain the study, but such failures will not interfere with their eligibility in the study.
- 3) The study partner subject signs the study partner subject consent for participating in the study after staff have reviewed the following study details with each study partner subject: 1) the objective of the project; (2) description of timeline, the assessment procedure and components; (3) description of the environment where the assessments are conducted; (4) description of how the confidentiality regarding participant data will be protected; (5) description of the potential risk, relevant protections, and benefits of participating in the study. Note: If the intervention subject's in-person screening appointment is scheduled to occur before the study partner subject's secondary screening appointment, and the intervention subject is deemed ineligible, the study partner subject will not be consented to the study.

8. STUDY PROCEDURES

COVID-19 Safety Regulations:

To ensure appropriate safety precautions when conducting in-person study procedures, the process for conducting in-person visits outlined in the Guidance for Human Subject Research webpage (<https://www.urmc.rochester.edu/coronavirus/coronavirus-research/guidance-for-researchers/human-subjects-research.aspx>) will be followed. We will remain vigilant about any further changes to the research reboot guidance.

This study will screen participants and their study partner subjects in two steps (phone-screening and secondary interview, including capacity to consent and informed consent). Eligible participants and their study partner subjects will be enrolled, and participants will be asked to complete a baseline cognitive assessment, MRI scan, and blood draw. The participant will then be randomized and start their intervention program within two weeks. Each program will consist of 14 tDCS sessions over 4 weeks. Follow-up cognitive assessments and MRI scans will occur at 4- and 8- weeks after baseline.

Screening: Potential participants who respond to our recruitment strategies and initiate contact with us will be carefully screened for eligibility and safety through a 2-step screening process:

(1) Phone screening (approximately 20 minutes for intervention subject and partner subject)

respectively): Upon over-the-phone contact, staff conducting the screening will explain the study using the phone screening script, answer any questions. If the participant is interested, the staff member will obtain their verbal consent to be administered the phone screening questions by signing and dating the verbal consent for screening form. Staff will collect basic self-reported health history to check for obvious contraindications for MRI or tDCS and to ensure a homogenous sample. Responses to these basic health history related items may need to be confirmed by their physician to ensure safety of MRI procedure are met. Identification of a “study partner subject” willing to participate in the study with the participant. Administration of the Neuropsychiatric Inventory Questionnaire (NPI-Q, a short form version of the NPI) with the study partner subject (after obtaining verbal consent from the study partner subject to be asked these questions) will also be conducted as part of this brief initial screening step,

Secondary cognitive screening: During the secondary screening interview (approximately 1.5 hours for intervention subject and 0.5 hour for partner subject), capacity to consent and informed consent will be obtained from the participant and their study partner subject. Study staff will verify the accuracy of phone screen data and note any changes, administer demographic and comprehensive health history questionnaires, administer measures to assess presence of a clinical diagnosis of MCI (see **Table 1** for more information regarding measures used). Staff will also administer the full version of the Neuropsychiatric Inventory (NPI) with the study partner subject. Secondary screening should be completed within 3 months of phone screening. **Note:** For partner subjects, secondary screening may be completed over the phone, in which case informed consent and capacity to consent will be completed along with NPI. Once a study partner has passed the capacity to consent, blank versions of the consent form will be sent to the partner with a self-addressed, stamped return envelope, and be sent back signed. Coordinators will then verify partner signature, then sign and date each copy. A fully-executed copy of the consent form will then be sent back to the study partner. The intervention subject and study partner subject may complete their secondary screening appointments on separate dates if preferred.

We expect to invite 180-200 individuals for the secondary screening visit to enroll 40 fully eligible intervention subjects. 100-120 subjects are estimated to have signed consent forms but end up as screen failures or lose interest in the study.

Assessments: Fully eligible participants and their study partner subjects will be notified of their eligibility for the study. Baseline assessments need to be scheduled within one month of in-person cognitive screening. Participants will then be asked to complete baseline measures (assessment, MRI scan, and blood draw), after which they will be randomized to either the active or sham tDCS intervention condition. The blood draw may occur within 2 weeks (before or after) the baseline assessment and MRI scan. The beginning of the intervention phase will start within two weeks after the baseline assessment and blood draw. Follow-up cognitive assessments and MRI scans for each participant will occur within 2 weeks after completion of intervention (i.e., post-intervention assessment) and then 4 weeks after post-intervention assessment (i.e., follow-up assessment). We will allow 2 weeks to make up the follow-up assessment. At the same time points, study partner subjects will be administered the NPI, AES, and QOLAD. Follow-up assessments for study partners can also be conducted over the phone, at the partners discretion.

A detailed overview of data collection measures for screening and assessments can be found below in **Table 1**. To reduce the burden on participants, study partner subjects, and staff, as well as to avoid practice effects of cognitive measures, for individuals who are eligible for the study, their screening data will be used as baseline data; for those who are not eligible for the study, their screening data will only be used for summarizing the reasons for ineligibility.

Group assignment/randomization will be determined with a block-based matlab randomization.

Table 1: Study Measures I = intervention subject; P = partner subject

	Screening		Baseline	Interventions				Makeup Interventions (if needed)		Post-Intervention Assessments	
	Phone	In-Person		Week 1	Week 2	Week 3	Week 4	Week 5	Week 6	Immediate Post-Intervention	Final Post-Intervention
Study Activities											
Verbal Consent for Screening	I, P										
Inclusion/Exclusion (verified at In-Person)	I, P	I, P									
MRI Screening Form	I										
Informed Consent		I, P									
UBACC		I									
Demographics & background		I, P									
MoCA (V2)		I									
RAVLT		I (Lists C&D)								I (Lists A&B)	I (Lists C&D)
ADL-PI-self		I								I	I
PSS		I								I	I
PSQI		I								I	I
MFI		I								I	I
GDS-15		I		I	I	I	I	I	I		
AES		I, P								I, P	I, P
QoL-AD		I, P								I, P	I, P
Medications		I									
Medication changes										I	I
NPI-Q	P			P	P	P	P				
NPI (Full)		P								P	P
Examiner			I (Form A)							I (Form B)	I (Form C)
GDS-30		I								I	I
C-SSRS		I								I	I
STAI		I								I	I
BVMT-R		I (Form 1)								I (Form 2)	I (Form 3)
DOSPERT		I								I	I
CRASH		I									
Blood Draw with questionnaire		I									
MRI scan (& confirm MRI screen form)		I								I	I
Intervention (sham or active)			I	I - One session per each weekday	I - Two sessions per week		I - Makeup sessions (if needed)				
MATLAB computer task				I - During each intervention session							
SAM				I - Before and after each intervention session							
Fatigue scale				I - Before and after each intervention session							

Note: For further details regarding measures, please see **Section 4: Study Design**.

Blood collection and processing:

We will collect a single blood sample from each participant within 2 weeks of the baseline assessment (before or after), and prior to beginning tDCS intervention sessions. This blood collection visit will require a separate appointment from the baseline assessment and MRI scan. Study staff will schedule the blood collection with CRC staff and confirm the appointment with the participant. Participants will be reminded to fast for 8 hours prior to their blood draw but may drink water and should take all medications as prescribed. On the day of the blood collection appointment, study staff will meet the participant at CRC and CRC staff will collect blood following a venous-blood collection protocol. Study staff will also ask each intervention subject 3-questions related to their diet and health in the past week. A total of 20mL of blood will be collected – 12mL into two 6mL plasma (EDTA-treated) tubes, and 8mL into two 4mL BD red serum tubes. Blood will be processed and frozen in cryo-vials at CRC -80° F freezer. Once cryo boxes are full (due to lack of space for storage of multiple cryo-boxes in CRC) then cryo boxes will be transferred to 4W-156, bio-safety level lab 2 in School of Nursing for storage in -80° F freezer until analysis.

No individual research results will be provided to intervention subjects or study partner subjects in this study. However, aggregate group results will be disseminated to all subjects after study completion.

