Exploratory aim 2: Examine blood biomarkers at baseline for predicting cognitive and brain MRI biomarker responses to intervention. Blood neuropathological (amyloid beta [A β] 42, total tau [t-tau], and neurofilament light [NfL]) and neurotrophic biomarkers (brain-derived neurotrophic factor [BDNF], insulin growth factor-1 [IGF-1], and short-chain acylcarnitines [SCACs]) relate to cerebral amyloidosis, neurodegeneration¹⁷⁻¹⁹ and neurogenesis.^{20,21} Blood A β 42 may indicate cerebral amyloidosis,¹⁹ and blood t-tau, and NfL levels have been shown to reflect neurodegeneration across populations (older adults with AD, MCI, or normal cognition).^{17,18} Their blood levels also correlate with their cerebrospinal fluid (CSF) levels, as well as several neuroimaging biomarkers (amyloid plaques, AD-related brain atrophy, and brain hypometabolism).¹⁷⁻¹⁹ Decreased blood A β 42 and increased t-tau and NfL levels were also found in individuals with MCI or AD and were associated with cognitive decline and incident AD over time.¹⁷⁻¹⁹ Preliminary data from colleagues at the University of Minnesota demonstrated that increased baseline plasma t-tau levels correlated with greater cognitive decline in older adults with MCI over time.²² Moreover, plasma phosphorylated tau (p-tau) is a promising biomarker of neuronal injury. A recent study showed that plasma p-tau levels were better biomarkers for both acute and chronic traumatic brain injury than plasma t-tau levels alone - further providing evidence in support of blood biomarkers as surrogate endpoints for treatment responses in neurological conditions such as aMCI and AD.²³

Blood neurotrophic factors have been shown to cross the blood-brain barrier to increase hippocampal volume and memory.^{20,25-32} Higher plasma BDNF levels were linked to better memory, larger hippocampal volume, and reduced risk for AD.^{25,28,29} Whereas higher plasma IGF-1 levels were cross-sectionally associated with better cognition³³ and lower odds of AD,³⁴ longitudinal data have been inconsistent. However, a recent study showed that higher plasma levels of IGF binding protein-3 (IGFBP-3), which are essential for IGF-1 physiological action,³⁵ were associated with decreased risk for dementia.³⁰

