fMRI data will be collected using a gradient echo-planar imaging sequence. Participants will undergo a 5-minute resting-state scan at first, being instructed to relax with their eyes open, followed by a 5-minute event-design ‘target among distractors’ visual search task. For the task, participants fixate on a black screen for a constant inter-stimulus interval of 1000ms, follow by 5500ms presentation of the search pattern. Participants’ task is to search for target symbol “申” (which was present for 50% of trials), shown among 6 distractors (e.g., “由”, “甲”, etc.). Participants are instructed to press one of two response buttons to indicate whether the target was present or absent.

Secondary endpoints:

- Study partner-rated NPS (frequency and severity scores from NPI and NPI-Q⁴⁶).

Other measures:

- Cognitive functions will be measured using tests from three different versions of the computer-based battery Executive Abilities: Measures and Instruments for Neurobehavioral Evaluation and Research (EXAMINER);
- Paper-based measures of cognitive functioning will be measured using two versions of the Rey Auditory Verbal Learning Test (RAVLT, Lists A&B and C&D) and the Brief Visuospatial Memory

Test-Revised (BVMT-R, Forms 1-3);

- Functioning in daily life will be measured with the self-report version of the Activities of Daily Living-Prevention Instrument (ADL-PI-self).
- Fatigue across 5 domains (general, physical, mental, and reduced motivation & reduced activity) will be measured using the Multidimensional Fatigue Inventory (MFI);
- Sleep habits and quality of sleep will be measured using the total score from the Pittsburgh Sleep Quality Index (PSQI);
- Depression will be measured using both the 15- and 30-item versions of the Geriatric Depression Scale (GDS);
- Risk of suicide (current & past) and current suicidal ideation will be measured using Columbia Suicide Severity Rating Scale (C-SSRS);
- Anxiety will be measured using both the state and trait anxiety scales from the State-Trait Anxiety Inventory (STA);
- Perception of stress will be measured using Perceived Stress Scale (PSS);
- Apathy will be measured using the 18-item self-report and informant-rated Apathy Evaluation Scales (AES);
- Quality of life (QoL) across multiple life domains (including physical health, mood, relationships, activities, ability to perform tasks) will be measured using the 13-item self-report and informant-rated Quality of Life in Alzheimer's Disease scales (QOLAD);

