5. INCLUSION AND EXCLUSION CRITERIA

a) Inclusion Criteria:

1. Forty intervention subjects with MCI and comorbid NPS, which have worsened in the past 2 years (as rated by their study-partner subject's responses to the NPI-Q):
 - (1) In the past month, presence of ≥ 2 symptoms; and
 - (2) Compared to two years ago, having ≥ 1 pre-existing symptom whose severity rating has worsened, or having ≥ 1 new symptom;
2. Consensus diagnosis of “mild cognitive impairment due to Alzheimer’s disease” based on 2011 NIA-AA diagnostic criteria by the investigators based on screening information:
 - i. Memory deficits at screening: 1 standard deviation (SD) below age- and/or education- corrected population norms for the Rey Auditory Verbal Learning Test (RAVLT, Lists C&D);
 - ii. Global memory deficits at screening: Montreal Cognitive Assessment (MoCA, Version 2) total score within the range $18 \leq x \leq 26$, after educational adjustment;
 - iii. Preserved activity of daily living: ADL-PI-self total score ≤ 30 ;
 - iv. Absence of dementia.
3. Stable (same dosage, frequency, type) on memory medications for ≥ 3 months before screening;
4. Stable (same dosage, frequency, type) on any anti-depressants, antipsychotics, and/or anxiolytics for ≥ 7 days;
5. Community-dwelling: Intervention subjects live in homes or independent- and assisted-living facilities (i.e. – not nursing home residents, due to the large cognitive variability in nursing home residents);
6. Aged 60-89 years at screening;
7. English-speaking;
8. Adequate visual and hearing acuity for testing;
9. Verified tDCS and MRI safety: Intervention subject should not have any contraindications to either and pass safety screening questions for both (see exclusion section for more information);
10. Capacity to consent, based on responses and ratings to the UCSD Brief Assessment of Capacity to Consent (UBACC) form for this study;

11. Availability of a study partner subject who spends at least several hours per week with the intervention subject, supervises his/her care, and who is willing to accompany the intervention subject to some study visits and participate in the study;
12. Informed consent for study participation obtained by both the intervention subject and his/her study partner subject;
13. Agree to donate 20mL of blood at baseline, after fasting for at least 8 hours (only water and prescribed medicines).

Study partner subject inclusion criteria:

1. Age 18 years or older;
2. English speaking;

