17. DATA ANALYSIS PLAN

This is a pilot study for mechanistic understanding of the relationship between our previously discovered NPS-shared neural circuit and study partner-rated NPS. Results from the study will provide information for accurately calculating effect size for future clinical trial. Regardless, in addition to follow the rule of 12-20 subjects per group for a pilot clinical trial, we will calculate the sample size. The sample size calculation is based on the effect size of LPG related tDCS on visual attention performance ($f = 0.45$, $n = 36$). Additionally, the effect size of correlation between NPS-shared neural circuit and patient-report NPI-Q was $r^2 = 0.70$ in our previous study³ – here we use a much more conservative estimation at $r^2 = 0.20$, the sample size will be $n = 37$. All of these calculations are based on power at 0.80 and alpha at 0.05. For an 8-week follow up, we estimate 10% attrition rate. Therefore, we propose a total of 40 intervention subjects for the study.

Aim 1. Determine the effect of tDCS on NPS-shared neural circuit. H: After intervention, the active, relative to sham group will have greater increase in LPG activity, indexed by greater activation in LPG in response to visual attention task (H1a) and greater increase in resting FC strength between LPG and other regions within the NPS-shared neural circuit (H1b). To assess the activation pattern in LPG, we will conduct GLM analysis with the SPM software. The coefficients of GLM corresponding to LPG will be analyzed through hypothesis testing. We will first conduct a simple t-test to evaluate whether the intervention increases LPG activation for each group (at 4 or 8 weeks), and then a more powerful two sample kernel test will be used to test activations distribution difference between groups.⁵¹ Similarly, we will take the FCs between LPG and other regions as a multivariate covariate and apply the two-sample kernel test to evaluate group difference in the change of LPG FC pattern after intervention (at 4 or 8 weeks). In addition, simple multiple testing for each connection will be used as a screening procedure to identify a subset of connections included in the kernel test.

Aim 2. Determine the relationship between NPS-shared neural circuit and study partner-report NPS.

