Exploratory aim. Examine the relationship between (a) NPS and (b) the coherence between structural and functional aspects of the NPS-shared neural circuit. We will conduct a connectome-based analysis to find structural connections that are unique to severity of NPI. The TN-PCA method⁵³ will be used to correlate with severity of NPI. We can replace the high dimensional tensor network summarizing an individual's brain connectome with a K-dimensional vector of brain PC scores; these scores can be used for visualizing variation among individuals in their brain connectomes and in statistical analyses studying relationships between structural and functional aspects of NPS-shared circuit and covariates. We will compare similarities of involved brain regions of NPS circuit for FC and WM across the entire sample at baseline. Quantitatively, we will use the Dice similarity coefficient to evaluate the percentage of overlapped regions. **To examine whether tDCS' effects on NPS-shared neural circuit and study partner-rated NPS depend on baseline WM integrity,** first we will compare the correlations between FC (at different time points) and baseline WM integrity on the overlapped regions between active vs. sham tDCS groups. We expect to see a higher correlation between FC and WM in active group in later time points. Next, using SVR described earlier⁵² we will examine the relationship between the sample's features (baseline WM tracts) and outcome (change of NPI severity or frequency scores).

Blood analysis plan: We will compare AD pathology markers from blood with changes of NPS, cognitive measures, and MRI data using correlational analyses. We will also examine if individuals with positive AD pathology respond differently to tDCS compared to those with negative AD pathology using ANOVA.

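### The screening RAVLT that qualifies people for entry is also the RAVLT baseline, which modestly biases the pooled correlation of blood markers with RAVLT change

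*Combined protocol and SAP*

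**What the plan says.** Section 5, inclusion criterion 2.i, sets the entry rule: "Memory deficits at screening: 1 standard deviation (SD) below age- and/or education- corrected population norms for the Rey Auditory Verbal Learning Test", using Lists C&D. The particular RAVLT score is not named.

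Section 8 (Assessments) reuses that measurement: "for individuals who are eligible for the study, their screening data will be used as baseline data". The reasons given are lower burden and avoidance of practice effects. Table 1 agrees. RAVLT appears at in-person screening and at the two post-intervention visits, with no entry in the Baseline column. EXAMINER Form A is the cognitive test placed in that column.

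Section 4 lists RAVLT among the other measures: "Paper-based measures of cognitive functioning will be measured using two versions of the Rey Auditory Verbal Learning Test".

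Exploratory aim 2 in Section 1 is to "Examine blood biomarkers at baseline for predicting cognitive and brain MRI biomarker responses to intervention". The blood analysis plan in Section 17 has two sentences on method. The first is "We will compare AD pathology markers from blood with changes of NPS, cognitive measures, and MRI data using correlational analyses". The second is "We will also examine if individuals with positive AD pathology respond differently to tDCS compared to those with negative AD pathology using ANOVA". Neither mentions an arm term, a baseline adjustment or regression to the mean, and the form of the ANOVA is not given.

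**The concern.** Selecting on a low screening score favours people whose measurement error that day was negative. Their next score tends to rise even if nothing has changed, and it does so with any word list, so alternate forms do not prevent it.

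The less obvious consequence concerns the markers. Among those admitted, people with better true memory could only pass the cut through a larger downward error, so they rebound more. Change then correlates with true memory although nobody changed, and so does any marker that tracks memory level. Section 1 itself describes several candidate markers as related to memory or cognition; BDNF is one.

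At stake is the reading of exploratory aim 2 for RAVLT. A marker that only reflects memory level could look like a predictor of response to stimulation.

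**Working it through.** **The plan's nearest figure.** No sample size is given for the marker analysis. The closest calculation is the correlation with r² = 0.20, for which Section 17 gives n = 37 and adds: "All of these calculations are based on power at 0.80 and alpha at 0.05". By Fisher z, two-sided: ((1.960 + 0.842)/atanh(√0.20))² + 3 = (2.802/0.4812)² + 3 = 36.9, so 37. This reproduces. The point below does not depend on it.

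**Inputs from the documents.** Cut at -1 SD; 40 enrolled; 10% attrition, so 40 × 0.9 = 36 at follow-up; alpha 0.05, taken as two-sided.

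**Inputs assumed, because the documents give none.** Retest correlation ρ = 0.6-0.8; mean RAVLT of those screened μ = 0 to -1 SD, extended to -2 SD; marker correlation with true memory m = 0.3 or 0.5.

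**Model.** Screening score Y1 = T + e1 and later score Y2 = T + e2, total SD 1, Var(T) = ρ, independent errors with variance 1 - ρ, no treatment effect and no true change. People enter if Y1 ≤ -1. Let c = -1 - μ, λ = φ(c)/Φ(c) and V = 1 - cλ - λ² (the variance of Y1 among those selected). Among those selected:

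- mean of Y2 - Y1 = (1 - ρ)λ
- Cov(marker, change) = m√ρ(1 - ρ)(1 - V)
- Var(change) = 2(1 - ρ) - (1 - ρ)²(1 - V)
- Var(marker) = 1 - m²ρ(1 - V)

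**Worked case** (μ = 0, ρ = 0.6, m = 0.5). λ = 0.2420/0.1587 = 1.525 and V = 1 + 1.525 - 2.326 = 0.199. Gain = 0.4 × 1.525 = 0.61 SD. Covariance = 0.5 × 0.775 × 0.4 × 0.801 = 0.124. Correlation = 0.124/√(0.672 × 0.880) = 0.161. At n = 40, atanh(0.161) × √37 = 0.99, so the 5% test rejects about 17% of the time.

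| μ | ρ | Spurious gain (SD) | r at m = 0.3 | Rejection, n = 36 / 40 | r at m = 0.5 | Rejection, n = 36 / 40 |
|---|---|---|---|---|---|---|
| 0 | 0.6 | 0.61 | 0.093 | 8.3% / 8.7% | 0.161 | 15.5% / 16.8% |
| 0 | 0.8 | 0.31 | 0.073 | 7.0% / 7.3% | 0.129 | 11.5% / 12.4% |
| -1 | 0.6 | 0.32 | 0.072 | 7.0% / 7.2% | 0.124 | 11.1% / 11.8% |
| -1 | 0.8 | 0.16 | 0.057 | 6.2% / 6.4% | 0.100 | 8.9% / 9.3% |
| -1.5 | 0.6 | 0.20 | 0.057 | 6.2% / 6.4% | 0.098 | 8.7% / 9.2% |
| -1.5 | 0.8 | 0.10 | 0.046 | 5.8% / 5.9% | 0.079 | 7.4% / 7.7% |
| -2 | 0.6 | 0.12 | 0.040 | 5.6% / 5.7% | 0.069 | 6.8% / 7.0% |
| -2 | 0.8 | 0.06 | 0.032 | 5.4% / 5.4% | 0.055 | 6.2% / 6.3% |

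**Checks by simulation** (20,000 trials per scenario).

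- A marker unrelated to memory (m = 0) shows no spurious correlation and rejects about 5% of the time.
- The active-minus-sham difference in change is 0.00 throughout.
- A separate RAVLT taken after eligibility, used as baseline, brings the mean change and the marker correlation to about 0 and rejection to about 5%.
- A marker-by-arm interaction rejects about 5% of the time, because randomisation puts the same artefact in both arms.

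**Does covariate adjustment rescue the pooled correlation?** The partial correlation of marker with later RAVLT given the screening score is m√ρ(1 - ρ)/√[(1 - m²ρ)(1 - ρ²)]. For ρ = 0.6-0.8 it is 0.09-0.12 at m = 0.3 and 0.17-0.21 at m = 0.5, which is larger than the raw bias. The screening score measures memory with error, so the marker still carries information about true memory after adjustment.

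**The case against.** The strongest reply is that the effect is small and the setting exploratory. RAVLT is one of many other measures in the second exploratory aim of a 40-person Stage 0 study, and reusing screening data is a deliberate choice to limit burden and practice. That stands, and it limits the weight of the point.

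The size also depends on unknowns. At a marker-memory correlation of 0.1-0.2, rejection is only about 5.1-6.6%. Section 6 says that recruitment is mainly through clinics, so those screened may average well below the norm, which shrinks the artefact. The MoCA floor of 18 and the exclusion of dementia limit selection from below and are not modelled. The entry score is unnamed, so the analysed score might be a different RAVLT index. All of this stands.

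The ANOVA sentence may be meant as a marker-by-arm test, in which the artefact largely cancels. That is a fair reading, but the plan does not say so, and the correlational sentence beside it is not such a test.

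Table 1 is partly displaced as extracted, so the visit at which the other tests are given should be confirmed. The RAVLT chain does not rest on the table alone: criterion 2.i and the Section 8 sentence establish it.

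A reader might infer that the trial is set to report a false benefit of stimulation, or false memory gains in both arms. The documents do not support either reading. Both arms pass the same entry rule, and the within-group changes described in Section 17 belong to the NPS mixed models; no within-arm RAVLT analysis is specified. Nor is anything shown here for ADL-PI-self, which also has an entry cut-off but was not examined.

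**Conclusion.** The concern holds in a limited form. RAVLT change contains regression to the mean created by the entry rule, and the pooled marker-change correlation for RAVLT is biased for markers related to memory level. With retest correlation 0.6-0.8, no true change and a screened mean of 0 to -1 SD, the spurious gain is 0.16-0.61 SD. The spurious marker correlation is about 0.06-0.09 at a marker-memory correlation of 0.3 (rejection about 6-9%) and 0.10-0.16 at 0.5 (about 9-17%). With a screened mean of -1.5 to -2 SD, rejection is about 5-9%. These ranges rest on assumed inputs.

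This does not make a false marker finding likely. It means that a weak positive RAVLT result could not be separated from the entry rule. The active-sham comparison and the primary and secondary endpoints are unaffected. It is a minor point, worth correcting because correction is cheap.

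**What to change.** Amend the blood analysis plan in Section 17:

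1. Make EXAMINER change the lead cognitive outcome for the marker-change correlations. It is first given at the baseline visit and is not an entry criterion. BVMT-R may be secondary, with a note that Table 1 places its first form at the same screening visit as the qualifying RAVLT, so a shared poor day could leave a smaller residue.
2. For RAVLT, test marker prediction as a marker-by-arm interaction, and state that the ANOVA on AD-pathology status takes this form. Report RAVLT itself as the active-minus-sham difference adjusted for the screening score.
3. State that neither a pooled marker-change correlation nor a within-arm gain on RAVLT will be read as response, and that adjusting the pooled correlation for the screening score does not remove the bias.

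The cost is a few sentences and no new data or visits. The downside is power: at n = 40 the interaction test has less than a pooled correlation. RAVLT need not be dropped.
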